
- Secondary – Efficacy
 
Pharmacokinetics and Pharmacodynamics
	
 • Changes from baseline through End of Trial Visit (Week 14) in: 
 ◦ Physical examinations ◦ Vital signs ◦ ECGs ◦ Safety laboratory parameters (full blood count including white differential count, clinical chemistry, thyroid hormones, urinalysis, and faecal occult blood test) ◦ Development of anti-drug antibodies against BT063 (anti-BT063) ◦ Immunological status of potential viral and bacterial infections (HBV, HCV, HIV, tetanus, diphtheria tuberculosis) ◦ EBV / CMV Serology ◦ Premature withdrawals • 50% improvement of swollen/tender joints or 50% improvement in CLASI Activity score at week 14 and week 28, depending on which was the more severe manifestation at baseline. • Percent changes in SLEDAI-2K scores from baseline to week 14 and at week 28 • Flare rate and severity at week 14 and week 28 based on BILAG index A or B (flare is defined as the presence of 1 or more new BILAG A scores or 2 or more new BILAG B scores.) • Time to first flare • Number of patients requiring an increase in oral glucocorticosteroid dose before week 14 • Physician's Global Assessment, Functional Assessment of Chronic Illness Therapy – Fatigue (FACIT-F) and SF-36v2 Physical Component Score (PCS) at week 14 and week 28 • ECLAM at week 14 and week 28 
Based on PK/PD findings at protocol-defined time points:
 
 • Pharmacokinetics: 
 - BT063 serum concentration - Maximum serum concentration (C_{max}) - Time to maximum serum concentration (t_{max}) - Area under the concentration-time curve from time 0 to the last observable concentration at time t (AUC_{0-t}) - Elimination half-life ($t_{1/2}$) - Apparent terminal-phase disposition rate constant (λ_z) - Total body clearance from serum (CL)
--	---

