11.4 Previous and Concomitant Medication or Treatment

Subjects should be on stable doses of concomitant medication for SLE activity maintenance and symptom control (e.g., azathioprine, methotrexate, leflunomide, mycophenolate mofetil, cyclosporine, antimalarials such as chloroquine or hydroxychloroquine, steroids, NSAIDS/pain medication), without change in the type or dose of the drug used during the 8 weeks prior to baseline (for steroids and NSAIDs/pain medication 2 weeks) with the expectation that there will be no need for change in concomitant medication until the End of Treatment visit (ideally throughout the whole study); however, if the subject is taking an oral glucocorticosteroid at a dose higher than equivalent to 20 mg prednisone/day, and planning to reduce the dose of glucocorticosteroid, the dose can be titrated during the screening period so that the subject has been on at most, a 20 mg/day dose of 2 weeks by day 0 (baseline; i.e., first BT063 dose).

Concomitant medications should not exceed the doses outlined in the summary of product characteristics (SPC) or standards for SLE management; except for oral glucocorticosteroids which are limited to a dose equivalent to 20 mg prednisone/day.

All previous and concomitant medications will be recorded in the appropriate sections of the eCRF.

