11.5 Prohibited Medication or Treatment

Medication other than allowed SLE treatments that is considered necessary for the subject's safety and well-being may be given at the discretion of the investigator and recorded in the appropriate sections of the eCRF. Investigators are encouraged to discuss the introduction of any restricted medications with the Sponsor or its representative.

Medications that are restricted or have special allowances during the study are listed in [Table 11.1](#). These restrictions begin at screening and are to be followed through the End of Treatment Visit at W14. During the 14-week follow-up period, certain medications may be administered at the investigator's discretion. However, no new medications for SLE should be started at any time during the study.

Table 11.1: Treatment Restrictions

Treatment	Restriction or Allowance
Glucocorticosteroids:	
Oral Glucocorticosteroids: stable dose \leq 20.0 mg prednisone daily or equivalent for at least 2 weeks prior to baseline and through the End of Treatment Visit at week 14. At most two short courses of an increased dose of oral glucocorticosteroids (i.e., 5 days) are allowed between week 4 and week 12 for management of flares. During the follow-up period these medications may be administered at the investigators discretion.
 
Intramuscular or intra-articular Glucocorticosteroids: not permitted in the 4 weeks prior to screening and during the entire study. If necessary, 1 intra-articular steroid injection is allowed, but the treated joints cannot be assessed within 4 weeks.
 
Intravenous Glucocorticosteroids (pulse therapy): not allowed within the 6 months before screening and during the entire study.
 
Inhaled and topical Glucocorticosteroids: use of topical steroids is allowed, but not within 24 hours before assessment.

Antimalarial drugs: hydroxychloroquine/ chloroquine	Stable dose levels up to the highest dose defined by the SPC for treatment of SLE are allowed during the 8 weeks prior to baseline and through the End of Treatment Visit at week 14. During the follow-up period these medications may be administered at the investigators discretion.

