15.2.5 Efficacy Analysis

The efficacy endpoints in this study are as below:

- 50% improvement of swollen/tender joints or 50% improvement in CLASI score at week 14 and at week 28, depending on which endpoint was the more severe manifestation at baseline.
- Percent changes in SLEDAI-2K scores from baseline to week 14 and at week 28
- Flare rate and severity at week 14 and week 28 based on BILAG index A or B (flare is defined as the presence of 1 or more new BILAG A scores or 2 or more new BILAG B scores.)
- Time to first flare
- Number of patients requiring an increase in oral glucocorticosteroid dose before week 14
- Physician's Global Assessment at week 14 and week 28
- Fatigue (FACIT-F) and SF-36v2 Physical Component Score (PCS) at week 14 and week 28
- ECLAM at week 14 and week 28

Efficacy endpoints will be summarized using descriptive statistics by visit and treatment group. Change from baseline will be calculated as post-baseline value minus baseline value. Percentage change from baseline will be calculated as (post-baseline value – baseline value)/baseline value ×100(%). Efficacy analysis will be performed on the ITT and PP populations.

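### The Week 28 joint/CLASI response carries no medication condition, although doses of background SLE drugs are left to the investigator after Week 14 and no endpoint counts increases from then on

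*Protocol*

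**What the plan says.** **Endpoint.** The synopsis lists "50% improvement of swollen/tender joints or 50% improvement in CLASI Activity score at week 14 and week 28", whichever manifestation was the more severe at baseline. Section 15.2.5 repeats it: "50% improvement of swollen/tender joints or 50% improvement in CLASI score at week 14 and at week 28". Neither place mentions concomitant medication.

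**Medication rules.** Section 11.5 introduces Table 11.1 with "These restrictions begin at screening and are to be followed through the End of Treatment Visit at W14". The rows for oral glucocorticosteroids, antimalarials, immunosuppressives and NSAIDs/coxibs then each carry the sentence "During the follow-up period these medications may be administered at the investigators discretion". Section 11.4 expects no change in SLE medication up to End of Treatment, and only ideally after that.

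**Limits that remain in follow-up.** Section 11.5 adds "However, no new medications for SLE should be started at any time during the study". Table 11.1 bars IV and IM steroids, IV cyclophosphamide, rituximab, belimumab, IVIg and plasmapheresis for the whole study. Section 11.4 holds concomitant drugs to label or standard doses, "except for oral glucocorticosteroids which are limited to a dose equivalent to 20 mg prednisone/day".

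**What is counted.** One endpoint counts a medication change: "Number of patients requiring an increase in oral glucocorticosteroid dose before week 14". The flare endpoint at Weeks 14 and 28 rests on BILAG grades: "flare is defined as the presence of 1 or more new BILAG A scores or 2 or more new BILAG B scores".

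**What is recorded.** Concomitant medication is recorded at Visit 13 (Week 20) and Visit 14 (Week 28), Sections 13.1.13 and 13.1.14.

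**The concern.** Up to Week 14 the protocol treats background therapy as something that can distort the efficacy reading. It requires stable doses, permits at most two short steroid courses (Weeks 4 to 12), counts steroid increases, and excludes an injected joint from assessment for 4 weeks. The same response is then read at Week 28, after 14 weeks in which the dose-stability rule and the count no longer apply.

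A subject whose disease returns after dosing stops, and whose prednisone or azathioprine is then raised, can reach 50% improvement at Week 28. That subject is tabulated in the same way as one whose improvement lasted on unchanged treatment. At stake is the reading of the off-drug result. The dose justification (Section 11.1.3) and the benefit section (13.5.1) both cite inactive disease at the end of follow-up with the murine predecessor, so a Week 28 response is likely to be read as a sign of lasting effect.

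**Working it through.** The protocol gives no rate, effect size or power for this endpoint (Section 15.1), so there is no stated figure to reproduce. The check sets the rules side by side and then bounds what can be bounded.

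**1. Rules by period (Sections 11.4, 11.5 with Table 11.1, 15.2.5)**

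| Item | To Week 14 | Weeks 14–28 |
|---|---|---|
| Oral steroids | stable, at most 20 mg/day, limited short courses | investigator's discretion |
| Antimalarials, immunosuppressives, NSAIDs | stable | investigator's discretion |
| New SLE drug | barred | barred |
| IV/IM steroid, IV cyclophosphamide, rituximab, belimumab, IVIg, plasmapheresis | barred | barred |
| Steroid-increase count | yes | none |
| Count for other classes | none | none |
| Joint/CLASI response | read at Week 14 | read at Week 28, same definition |

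What remains open after Week 14 is a dose increase of a drug already in use. This is an inference from the end of the stable-dose rule together with the ban on new drugs only. The table does not say it in those words.

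**2. Does the flare endpoint pick it up?** It counts BILAG grades, not drugs. The BILAG form (Appendix E) covers the last 4 weeks. After Visit 12 (Day 98), the next visits are Day 140 and Day 196.

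- Look-back at Day 140: from 140 − 28 = Day 112. Uncovered: Days 98–112 (Weeks 14–16), 14 days.
- Look-back at Day 196: from 196 − 28 = Day 168. Uncovered: Days 140–168 (Weeks 20–24), 28 days.
- Total: 42 of 98 days = 43%.

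These are nominal days; the visits have windows. A flare that begins and is treated successfully within a gap may never be graded.

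**3. Weight of one subject.** With 12 BT063 and 6 placebo per part, 1/6 = 16.7 points and 1/12 = 8.3 points. If placebo is pooled over both parts, 1/12 = 8.3 points.

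**4. Drug left at Week 28.** The last dose is at Day 84 and Visit 14 at Day 196, so 112 days. The half-life is 20–26 days in healthy subjects (Section 11.1.3).

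- 112/26 = 4.31 half-lives, 0.5^4.31 = 5.0%
- 112/20 = 5.60 half-lives, 0.5^5.60 = 2.1%

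This does not measure the bias. It shows that Week 28 is an off-drug reading.

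**5. Illustration of the bias (all rates assumed).** Let p be the response without escalation, e the share of non-responders escalated in Weeks 14–28, and s their response rate afterwards. Observed response = p + (1 − p) × e × s.

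- p = 50% vs 20%, e = s = 0.5 in both arms: 62.5% vs 40.0%. The difference is 22.5 points instead of 30.
- Equal e (0.25–0.75) and s (0.3–0.7) in both arms: the share of the difference kept is 1 − e × s, from 1 − 0.075 = 92.5% down to 1 − 0.525 = 47.5%.
- Unequal escalation, e = 0.5 on BT063 and 0.25 on placebo, s = 0.5: 0.5 + 0.5 × 0.25 = 62.5% vs 0.2 + 0.8 × 0.125 = 30.0%. The difference is 32.5 points, above 30.

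So the difference can shrink or grow, and nothing in the protocol says which.

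**The case against.** The strongest reply is that how to handle changed background therapy is SAP detail. Section 15.2.9 defers analysis detail to the SAP, and the remedy is only an added table. It is fair that a SAP, not seen here, could add such a rule. But the protocol itself fixes the endpoint definition, the Week 14 end of the stable-dose rule and the cut-off of the steroid count, and the problem comes from those three together.

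Second, freedom to treat active lupus after dosing ends is reasonable, and the as-observed endpoint honestly describes outcomes under it. That stands, which is why the as-observed table should stay.

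Third, little turns on it. The efficacy objective is 3 months of treatment (Section 7), durability is not a stated objective, no tests are planned, and the Part II dose choice rests mainly on data to Week 14. The interim analysis does include available follow-up visits (Section 8.1), so some such data can reach the DSMB. The reply still stands on priority. SLEDAI-2K, PGA, FACIT-F, SF-36v2 and ECLAM at Week 28 share the feature, so the count by arm would help there too.

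Three stronger readings are tempting and should be resisted:

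- *The flare endpoint misses an increase prompted by a single new B grade.* The endpoint's definition needs one new A or two new B grades, but Section 14.2.2.3 calls a single rise to B a moderate flare, and the endpoint includes severity. The gap lies in the look-back windows and in counting grades rather than drugs.
- *A dose increase is certainly no deviation and stays in the per-protocol set.* The documents do not say so. Sections 15.2.1 and 16.3.1 leave major/minor classification to the sponsor, the statistician and the blinded review.
- *The 20 mg/day steroid ceiling clearly bounds the increase.* Section 11.4 states it without a time limit, but whether it binds under the follow-up discretion in Table 11.1 is not spelled out.

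**Conclusion.** The point holds in a limited form. As written, the Week 28 joint/CLASI response mixes any lasting effect of BT063 with increased doses of background drugs, and no endpoint shows how often such increases occurred. It rests on one inference, that discretion after the stable-dose rule ends includes raising the dose of a drug already in use.

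The size and direction of the bias are unknown. The figures fixed by design are the step per subject (16.7 points on placebo, 8.3 on BT063 within a part) and the nominal 42 of 98 days outside any BILAG look-back. A reader might infer that the Week 28 result is biased in favour of BT063, or that the Part II dose decision is compromised. The documents support neither. This is a low-priority improvement to a secondary, descriptive endpoint.

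**What to change.** Keep the as-observed Week 28 responder table and make these additions:

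- **A second Week 28 responder table.** Count as a non-responder any subject who, between Week 14 and Week 28, had an oral steroid, antimalarial or immunosuppressive raised above the baseline dose, or newly started for SLE.
- **A count by arm.** Extend the steroid-increase count to Weeks 14–28 and to antimalarials and immunosuppressives.
- **NSAIDs as a count only.** An NSAID may be raised for a reason other than lupus, so an increase should not make a subject a failure.

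The reference should be the baseline dose, not the Week 14 dose. Otherwise a subject who tapers and returns to baseline would be classed as a failure.

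Cost: one extra table and one count, from medication data already recorded at Visits 2, 13 and 14, with no new visits or assessments. This assumes that the eCRF holds doses and dates for these drugs; the existing steroid-increase endpoint already needs them for steroids. The downside is that some subjects who would have responded anyway count as failures in the added table, which is a reason to show both tables together.

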11.6 Risks and Precautions

Detailed information about the risks and precautions are described in the Investigator's Brochure (IB). Further information is given in [Section 13.5, Benefit-Risk Evaluation](#).

12 STUDY POPULATION

12.1 Study Population, Diagnosis and Number of Subjects

12.1.1 Sex Distribution

Since SLE affects women more than men, it is expected that approximately 90% of enrolled study subjects will be women and approximately 10% will be men. A total of 36 subjects will be enrolled in Study 990 (18 each in Part I and Part II) No specific measures will be taken to control the distribution of sex in the enrolled population.

12.1.2 Diagnosis

Adult subjects of both sexes with a diagnosis of SLE as defined by the ACR criteria ([Appendix B](#)) are eligible for inclusion in this study if at least 4 of the 11 criteria are met during the 3 months before screening.

Subjects must have moderate to severe SLE disease defined by a SLEDAI-2K total score of at least 6. Skin and joints must be affected by the disease and contribute to SLEDAI-2K scoring.

Skin involvement measured by CLASI score must reach at least 5 or alternatively at least 5 of 66/68 joints must have pain and signs of inflammation present (i.e., swelling and/or specific tenderness at the joint lining).

For further definition of the study populations please refer to the inclusion and exclusion criteria in [Section 12.2](#) and [Section 12.3](#).

12.2 Inclusion Criteria

Only subjects meeting all of the following inclusion criteria will be considered for study inclusion:

Inclusion Criteria	Rationale	Screening	Baseline
1. Able to provide written informed consent and/or consent obtained from a legally acceptable representative (as required by IRB/IEC) prior to the initiation of any protocol-required procedures.	Administrative	•	
2. Diagnosis of SLE as defined by ACR criteria (Appendix B) such that ≥ 4 of the 11 criteria are met for ≥ 3 months before screening	Medical	•	
3. Moderate to severe SLE disease activity at screening and baseline demonstrated by SLEDAI-2K total score ≥ 6 , including skin and joint involvement	Medical	•	•
4. Regarding skin and joints, both need to be involved, and either skin should be involved according to CLASI Activity score ≥ 5 or at least 5 of 66/68 joints with pain and signs of inflammation present at screening and baseline (joints suspected or known to have ischemic osteonecrosis are not to be taken into consideration)	Medical	•	•
5. No change in concomitant medication for SLE activity maintenance and symptom control (e.g., azathioprine, methotrexate, leflunomide, mycophenolate mofetil, cyclosporine, antimalarials such as chloroquine or hydroxychloroquine, glucocorticosteroids, pain medication, e.g. nonsteroidal anti-inflammatory drugs [NSAIDs] or paracetamol) regarding type of medication and dose level for at least 8 weeks prior to baseline (for steroids and NSAIDs/pain medication 2 weeks) and with the expectation that there will be no need for change in concomitant medication until the End-of-Treatment visit (ideally throughout the whole study);	Medical	•	•

Inclusion Criteria	Rationale	Screening	Baseline
however, if the subject is taking an oral glucocorticosteroid at a dose higher than equivalent to 20 mg prednisone/day, and planning to reduce dose of glucocorticosteroid, the dose can be titrated down during the screening period so that the subject has been on, at most, a dose equivalent to 20 mg prednisone/day for 2 weeks by day 0 (baseline; i.e., first BT063 dose)			
6. The dose of concomitant medication for SLE activity maintenance and symptom control (e.g., azathioprine, methotrexate, leflunomide, mycophenolate mofetil, cyclosporine, antimalarials such as chloroquine or hydroxychloroquine, glucocorticosteroids, pain medication, e.g. nonsteroidal anti-inflammatory drugs [NSAIDs] or paracetamol) should not exceed the doses outlined in the summary of product characteristics (SPC) or standards for SLE management. For oral glucocorticosteroids maximal allowed dose is limited to a dose equivalent to 20 mg prednisone/day. NSAIDs should not be taken within 24 hours, paracetamol not within 12 hours prior to study visits	Medical	•	•
7. Positive ANA at screening (as per central laboratory results)	Medical	•	
8. Age \geq 18 and \leq 75 years at screening	Medical	•	
9. Body mass index \geq 18 and \leq 35 kg/m ²	Medical	•	
10. Normal ECG, i.e., no acute and clinically relevant abnormalities	Medical	•	

12.3 Exclusion Criteria

Subjects having any of the following criteria, either at screening or at baseline, will not be included in the study:

Exclusion Criteria	Rationale	Screening	Baseline
1. Has active, severe SLE disease activity which involves the renal system and/or active, severe, neuropsychiatric SLE, defined as any neuropsychiatric element scoring BILAG level A disease.	Medical	•	•
2. Diagnosed psoriasis	Medical	•	
3. Presence or history of malignancy within the previous 5 years (except for successfully treated non-metastatic cutaneous squamous or basal cell carcinoma and/or localized carcinoma in situ of the cervix)	Medical	•	
4. Received any vaccination within 8 weeks prior to screening (except for influenza or tetanus booster)	Medical	•	

Exclusion Criteria	Rationale	Screening	Baseline
5. History of more than 3 infections during the last 12 months requiring IV antibiotic treatment	Medical	•	
6. Systemic antibiotic treatment within 2 weeks before the baseline visit	Medical		•
7. A positive diagnosis for any of the following: 
 • Acute or chronic viral hepatitis B (isolated positivity to hepatitis B surface antibody [anti-HBs] is allowed as an indicator of a previous vaccination that will be confirmed in the subject's notes) or acute or chronic hepatitis C (positive to anti-hepatitis C antibodies or hepatitis C viral RNA) • Human immunodeficiency virus (HIV) or tested positive for tuberculosis as assessed by QuantiFERON® TB gold test (if the result is inconclusive it may be repeated once) • Acute, clinically relevant, or potentially recent infection with Herpes Zoster or Herpes Simplex (Type 1 and Type 2), EBV or CMV infection or reactivation at screening 	Medical	•	
8. Clinically significant hematologic abnormalities attributed to SLE: 
 • Haemoglobin < 8 g/dL • Platelets 50×10^9/L • Leucocytes $< 2 \times 10^9$/L 	Medical	•	
9. Active or history of inflammatory bowel disease (including active or history of colitis)	Medical	•	
10. Received the following medications: 
 • Rituximab within the last 48 weeks before screening • Belimumab within the last 12 weeks before screening • IV immunoglobulin within the last 12 weeks before screening • Intramuscular (IM) or intra-articular glucocorticosteroids within the last 4 weeks before screening • IV cyclophosphamide within the last 6 months before screening • IV glucocorticosteroids (pulse therapy) within the last 6 months before screening 	Medical	•	
11. Participation in another clinical study in the 90 days prior to baseline or within 5 half-lives of the investigated compound, whichever is longer; Participation in another clinical study during this study and/or previous participation in this study	Medical		•

Exclusion Criteria	Rationale	Screening	Baseline
12. Pregnant or nursing women or women who intend to become pregnant	Medical	•	•
13. Men or women not will to use effective contraception excluding women not of childbearing potential (Subjects who are sexually active women of childbearing potential or sexually active men who are not practicing 2 different methods of birth control with their partner during the study and for 4 months after the last dose of IMP or who will not remain abstinent during the study and for 4 months after the last dose. If using birth control, each couple must use 2 of the following precautions: vasectomy, tubal ligation, vaginal diaphragm, intrauterine device, birth control pill, birth control implant, birth control depot injections, condom, or sponge with spermicide. Women who are not of childbearing potential include those who are at least 1 year post-menopausal confirmed by follicle-stimulating hormone [FSH] levels or women who are surgically sterile.)	Medical	•	•
14. Known intolerance to immunoglobulins or comparable substances (e.g., significant vaccination reaction)	Medical	•	
15. Known intolerance to proteins of human origin	Medical	•	
16. Employee or direct relative of an employee of the CRO, the study site, or Biostest	Administrative	•	•
17. History of clinically significant drug or alcohol abuse within the last 12 months	Medical	•	
18. Any other significant acute or chronic illness or laboratory abnormality, which, in the opinion of the investigator, might compromise the safety of the subject or influence the outcome of the study and its objectives.	Medical	•	

